3.2 Rationale and risk/benefit assessment

3.2.1 Rationale for study design, doses and control groups

To address the goal of a comparative assessment of rosuvastatin/ezetimibe vs simvastatin/ezetimibe, the study design employs a parallel design with treatment groups formed by randomised allocation so that statistical inferences are valid. To characterise the additivity of ezetimibe and rosuvastatin, a sequential treatment 'before and after' design is incorporated, ie, the incremental contribution of ezetimibe is determined after addition to rosuvastatin. Prior studies with the top dose (40 mg) of rosuvastatin suggest that ezetimibe and rosuvastatin have additive effects on LDL-C lowering whether co-administered as 'initial therapy' or as the sequential addition of ezetimibe (Ballantyne et al 2007, Ose et al 2005, Stein et al 2005b).

The primary objective is constructed of 3 components. The statistical analytical plan specifies a 'family of tests' approach using the Hochberg procedure to adjust for the multiple comparisons and is detailed in Section 6. The second goal of the study, to characterise the additivity of ezetimibe and rosuvastatin, is a sufficiently independent objective, ie, no further adjustments for the number of comparisons is required.

Plasma LDL-C is an accepted measure for cholesterol lowering therapies and the change from baseline value allows for an approximate quantification of the magnitude of the treatment effect. To minimise variability of the baseline measure, the study design includes a pre-randomisation 6-week dietary lead-in period during which patients are instructed to follow therapeutic life-style measures (TLC diet) and to discontinue potential confounding lipid altering therapies (see Table 4). To minimise variability, the end of study treatment LDL-C measure is derived as the mean of the last 2 measures (after 4 and 6 weeks of combination treatment).

The study is conducted open-label, which allows for treatment with the fixed dose combination simvastatin/ezetimibe tablets (corresponding fixed dose rosuvastatin/ezetimibe tablets are not available). However, investigators and sponsor staff remain blinded to the objective efficacy measures (cholesterol values) as these are maintained by the central laboratory and can only be provided to study centre personnel following last patient completed, database lock and formal unblinding.

3.2.2 Risk/benefit and ethical assessment

All the patients in this study are at high CHD risk and are thus candidates for treatments capable of inducing substantial reductions in LDL-C and all receive such a treatment. The agents under study are marketed throughout the world and their efficacy and safety properties have been characterized accordingly. While there is not a marketed fixed dose rosuvastatin/ezetimibe combination product, rosuvastatin at its highest dose has been studied in co-administration with ezetimibe and this combination was generally well tolerated.

Dosing recommendations for statin therapy typically suggest starting at lower doses and escalating the dose as needed and as tolerated. In the clinical study setting the initiation of statin treatment at high doses has, however, generally been well tolerated (Crouse et al 2007, Nissen et al 2006), and the current study incorporates standard clinical and laboratory oversight measures that would support high dose initial statin treatment.

The risks associated with statin and dyslipidemia treatment are well described and include abnormalities in hepatic and renal function as well as myopathy and rhabdomyolysis. The study eligibility criteria and specified safety monitoring measures outlined in the clinical study protocol (CSP) are structured to minimise the risk for these adverse effects.

3.3 Selection of study population

3.3.1 Study selection record

Investigator(s) must keep a record of patients who were considered for enrolment but who were never enrolled in a screening log so as to characterise the population sampled for the study.

3.3.2 Inclusion criteria

At Visit 1 (Week -6)

For inclusion in the dietary lead-in phase, patients must fulfil all of the following criteria at Visit 1:

- 1. Provision of signed written informed consent
- 2. Male or female patients aged 18 years of age or older
- 3. A history of CHD or a CHD risk equivalent, clinical evidence of atherosclerosis (definitions given in Appendix G) or a 10-year Framingham risk score of >20% for CHD, as described in NCEP ATP III guidelines
- 4. The patient must have a reasonable likelihood of attaining LDL-C values of $\geq 130 \text{ mg/dL}$ to < 220 mg/dL at Visit 2, in the opinion of the Investigator. Based upon the experience of previous studies, the following guidance can be used in interpreting Visit 1 LDL-C results:
 - $\circ \geq 125 \text{ mg/dL} (3.24 \text{ mmol/L}) \text{ to } <220 \text{ mg/dL} (5.69 \text{ mmol/L}) \text{ in statin-naïve} patients (patients who have not taken any lipid-lowering therapy known to affect LDL-C in the 4 weeks prior to Visit 1)$
 - $\circ \geq 90 \text{ mg/dL} (2.33 \text{ mmol/L}) \text{ to } <180 \text{ mg/dL} (4.66 \text{ mmol/L}) \text{ in patients who have taken lovastatin, fluvastatin, or pravastatin within 4 weeks of Visit 1$
 - $\circ \geq 70 \text{ mg/dL} (1.81 \text{ mmol/L}) \text{ to } <160 \text{ mg/dL} (4.14 \text{ mmol/L}) \text{ in patients who have taken simvastatin, atorvastatin, rosuvastatin or any statin in combination with ezetimibe within 4 weeks of Visit 1$
- 5. Fasting TG concentrations <400 mg/dL (4.52 mmol/L)
- 6. Patients willing to follow all study procedures including attendance at clinics for scheduled study visits, fasting prior to clinic visits (all visits blood draws) and compliance with study treatment regimen

For inclusion in the biomarker research, patients must fulfil the following criterion:

• Provision of written informed consent for biomarker research

For inclusion in the genetic research, patients must fulfil the following criterion:

• Provision of written informed consent for genetic research. Any additional criteria are provided in Appendix K

If a patient declines to participate in the biomarker or genetic research, there will be no penalty or loss of benefit to the patient. The patient will not be excluded from other aspects of the study described in this CSP, so long as they consent.

Randomised treatment period

For inclusion into the randomised treatment phase of the study, patients must fulfil the following criteria:

- 1. Fasting LDL-C concentrations of \geq 130 mg/dL (3.36 mmol/L) to <220 mg/dL (5.69 mmol/L) at Visit 2
- 2. Fasting TG concentrations <400 mg/dL (4.52 mmol/L) at Visit 2

3.3.3 Exclusion criteria (for dietary lead-in and randomised treatment period)

At Visit 1 (Week -6)

Any of the following is regarded as a criterion for exclusion from the study:

- 1. Use of lipid lowering drugs and other prohibited concomitant medications from Visit 1 (see Section 3.7)
- 2. History of statin-induced myopathy, or serious hypersensitivity reaction to other HMG-CoA reductase inhibitors (statins), including rosuvastatin, simvastatin and/or a history of hypersensitivity to any components of ezetimibe
- 3. Pregnant women, women who are breast feeding, and women of childbearing potential who are not using chemical or mechanical contraception or have a positive serum pregnancy test (serum β-HCG analysis)
- 4. Patients considered to be unstable by the Investigator after the following events (event within 8 to 12 weeks of study entry (Visit 1) at the Investigators discretion): a myocardial infarction, recent episode of unstable angina, myocardial revascularisation [percutaneous transluminal coronary angioplasty (PTCA), coronary artery bypass graft (CABG) surgery or another revascularisation procedure] or a transient ischaemic attack (TIA) or stroke. (These patients should be on a statin and should not be entered into a washout phase, therefore they are unsuitable for this study)
- 5. Severe congestive cardiac failure (New York Heart Association [NYHA] Class IIIb or IV) (see Appendix H). (There is no evidence that these patients benefit from statin therapy)
- 6. Patients awaiting a planned myocardial revascularisation prior to Visit 1. (These patients require statin therapy and so a washout phase is not appropriate; therefore they are unsuitable for this study)

- 7. History of malignancy with the exception of resected basal cell or squamous cell carcinoma of the skin. Women with a history of cervical dysplasia will be permitted to enter the study provided they have 3 consecutive clear Papanicolaou (Pap) smears. (So that patients who are at risk of recurrence of malignancy requiring treatment are not included)
- 8. History of homozygous familial hypercholesterolaemia (the severity of hypercholesterolaemia in these patients usually dictates the need for individualised treatment regimens which can include phoresis)
- 9. History of alcohol or drug abuse within the last 5 years

3.3.4 Restrictions

Patients are instructed to adhere to the following restrictions during the study:

- 1. Avoid blood donation within 3 months of entering the study, during the study and for 3 months following study participation
- 2. To fast (water is permitted) for 8 hours before each study visit. Refrain from consuming alcohol and cigarette smoking on the morning of each of these clinic visits
- 3. Maintain their usual physical activities or exercise
- 4. Follow the NCEP TLC diet for the duration of the study (see Appendix I)
- 5. Not to take any of the disallowed medications outlined in Section 3.7

3.3.5 Discontinuation of patients from treatment or assessment

3.3.5.1 Criteria for discontinuation

Patients may be discontinued from study treatment and assessments at any time. Specific reasons for discontinuing a patient from this study are:

- 1. Voluntary discontinuation by the patient who is free at any time to discontinue his/her participation in the study, without prejudice to further treatment
- 2. Safety reasons as judged by the Investigator and/or AstraZeneca
- 3. If at any time, the patient experiences muscle pain, tenderness or weakness which is accompanied by CK >10 x ULN, study medication should be discontinued. See management of increased CK in Appendix D
- 4. If ALT (SGPT) >3 x ULN on 2 consecutive occasions at least 48 hours apart, withdrawal of study medication is recommended (see Appendix B)
- 5. Severe non-compliance to protocol as judged by the Investigator and/or AstraZeneca
- 6. Pregnancy
- 7. Deterioration in the patient's condition which, in the opinion of the Investigator, warrants study medication withdrawal
- 8. Incorrect enrolment, ie, enrolment in violation of the inclusion/exclusion criteria
- 9. Incorrect randomisation, ie, randomisation in violation of the inclusion/exclusion criteria, where the evaluation of the Study Team Physician and Investigator did not render it appropriate to allow the patient to continue the study

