Appendix Date				

Appendix C Guidance on Management of Elevated Transaminases and Suspected Liver Disease Clinical Study Protocol Appendix C Drug Substance Rosuvastatin Study Code D356FC00003 Appendix Edition Number 1.0 Appendix Date

GUIDANCE ON MANAGEMENT OF ELEVATED TRANSAMINASES AND SUSPECTED LIVER DISEASE

- ALT and other liver function tests should be measured at baseline and during the study as directed in the trial plan.
- Appropriate liver function tests should be measured at any other time if liver disease is suspected.
- A suitably-experienced physician should be involved in interpreting the results and deciding appropriate management for the subject. The physician should be alerted to the occurrence of any ALT values >3xULN and significantly out-of-range values for other liver function tests. The following questioning and follow-up investigations should be considered:
 - Clarify the nature, duration and intensity of relevant symptoms
 - Review possible predisposing factors, such as: alcohol intake, viral illness (consider performing serology), concomitant medications including any recreational drug use, travel, blood transfusion, sexual behaviour
 - Physical examination for jaundice and other signs of liver disease
 - Perform additional liver function tests, perhaps including ALT, AST, bilirubin, alkaline phosphatase, GGT, viral serology, prothrombin time
 - Diagnostic imaging, such as ultrasound, CT, or MRI
 - Arrange to review the subject and repeat liver function tests after a suitable interval depending on the clinical picture (perhaps 4-10 days), or earlier if symptoms of liver disease appear or worsen
- The Study Team Physician is available to give advice (see Emergency Contact details).
- Statin-related ALT elevation is considered to be clinically significant if ALT is increased to >3xULN on 2 consecutive occasions. If this occurs without an obvious reversible precipitating factor, or if on clinical grounds, statin-induced liver disease is diagnosed or suspected, it is recommended that statin therapy should be discontinued. In these circumstances, an appropriate adverse event should be recorded, and the Study Team Physician must be informed.
- Study treatment must not be restarted without discussion with the Study Team Physician

Clinical Study Protocol Appendix D				
Drug Substance	Rosuvastatin			
Study Code	D356FC00003			
Appendix Edition Number	1.0			

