Appendix Date				

Appendix D Guidance on Management of Muscle Symptoms and Increased Creatine Kinase (CK) Clinical Study Protocol Appendix D Drug Substance Rosuvastatin Study Code D356FC00003 Appendix Edition Number 1.0 Appendix Date

GUIDANCE ON MANAGEMENT OF MUSCLE SYMPTOMS AND INCREASED CREATINE KINASE (CK)

- Throughout the study, subjects should be instructed to promptly report unexplained muscle pain or weakness, particularly if associated with malaise or fever. If this occurs, creatine kinase (CK) should be measured as soon as possible.
- Also, if CK is found to be elevated >5xULN on routine testing, the subject should be questioned about muscle symptoms.
- A study site physician should be alerted to the occurrence of unexplained muscle symptoms and any CK values >5xULN, and must take immediate action if CK >10xULN.
- A suitably-experienced physician should be involved in deciding appropriate management for the subject, taking account of any local guidelines.
- The following questioning and follow-up investigations should be considered:
 - Clarify the nature, duration and intensity of any muscle symptoms
 - Review possible predisposing factors, such as: unaccustomed exercise (including decorating, gardening etc), heavy alcohol intake, viral illness (consider performing serology), concomitant medications and consider diagnosis of other conditions which can cause myopathy
 - Physical examination for muscle tenderness, weakness and rash
 - Measure CK again within a few days
 - Measure serum creatinine
 - Urinalysis (including myoglobin and sediment)
 - Arrange to review the subject again in 4 to 10 days, or earlier if symptoms of myopathy appear or worsen, or if the urine becomes very dark
- The Study Team Physician is available to give advice (see Emergency Contact details).
- Myopathy is defined as muscle aches or weakness in association with CK increased to >10xULN. If myopathy occurs without an obvious reversible precipitating factor, or if on clinical grounds, statin-induced myopathy is diagnosed or suspected, statin therapy should be discontinued. Myopathy should always be recorded as an adverse event, and the Study Team Physician must be informed.
- Study treatment should not be restarted without discussion with the Study Team Physician.

Clinical Study Protocol App	Clinical Study Protocol Appendix E						
Drug Substance	Rosuvastatin						
Study Code	D356FC00003						
Appendix Edition Number	1.0						

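### Section 3.3.5.1 and Appendix D give different stopping instructions for muscle symptoms with CK above 10xULN; the ALT recommendation also differs from Appendix C and cites the wrong appendix

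*Protocol*

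**What the plan says.** **CK, body.** Section 3.3.5.1 item 3 applies at any time in the study to muscle pain, tenderness or weakness "which is accompanied by CK >10 x ULN, study medication should be discontinued". It attaches no exception and adds: "See management of increased CK in Appendix D".

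**CK, appendix.** Appendix D states: "Myopathy is defined as muscle aches or weakness in association with CK increased to >10xULN". Its stopping sentence then reads "If myopathy occurs without an obvious reversible precipitating factor, or if on clinical grounds, statin-induced myopathy is diagnosed or suspected, statin therapy" should be stopped.

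**ALT, body.** Section 3.3.5.1 item 4: "If ALT (SGPT) >3 x ULN on 2 consecutive occasions at least 48 hours apart, withdrawal of study medication is recommended (see Appendix B".

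**ALT, appendix.** Appendix C regards a statin-related rise as clinically significant when ALT exceeds 3xULN twice in succession, with no minimum gap. It then recommends stopping the statin under this condition: "If this occurs without an obvious reversible precipitating factor, or if on clinical grounds, statin-induced liver disease is diagnosed or suspected".

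**Cross-references.** Appendix B contains further guidance on the definition of a serious adverse event and on the causality question. It has no ALT threshold and no liver management. Section 4.7.2.1 sends the reader to Appendix C for raised liver tests.

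**Precedence.** The only ranking clause, Section 7.5, puts the protocol above the clinical study agreement. Nothing ranks the body of the protocol against its appendices.

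**The concern.** A site that meets item 3 and follows its own cross-reference arrives at a differently conditioned instruction for the same clinical picture. This matters because Section 3.2.2 relies on the eligibility criteria and the specified safety monitoring to limit the risk of myopathy, rhabdomyolysis and hepatic abnormality, including when statins are started at high dose. Stopping criteria belong to that protection and should read one way. As written, two sites that each follow the protocol could handle the same patient differently.

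The ALT texts raise the same issue in a milder form. In addition, the reader of item 4 is sent to an appendix that says nothing about ALT.

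**Working it through.** No arithmetic applies and the plan states no figure on this point. The check sets the texts side by side and runs cases through them.

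**Step 1: are the triggers the same?** The numeric thresholds agree: CK above 10xULN in item 3 and Appendix D, and ALT above 3xULN twice in item 4 and Appendix C. The muscle symptoms nearly agree: item 3 lists pain, tenderness and weakness, and Appendix D's definition lists aches and weakness. The difference lies in the conditions attached to the triggers.

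**Step 2: what conditions are attached?**

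| | Section 3.3.5.1 | Appendix |
|---|---|---|
| CK: reversible-cause condition | none (item 3) | yes (D) |
| CK: strength | directive | directive once its condition is met |
| ALT: reversible-cause condition | none (item 4) | yes (C) |
| ALT: minimum gap between values | 48 hours | none |
| ALT: strength | recommendation | recommendation |
| What is stopped | study medication | statin therapy |
| Reference given in 3.3.5.1 | CK: D; ALT: B | ALT guidance is in C |

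**Step 3: run the cases.**

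- (a) Muscle symptoms, CK above 10xULN, an evident reversible cause such as unaccustomed exercise (one of the factors Appendix D asks the physician to review), statin myopathy not suspected. Item 3 calls for stopping. Appendix D's condition, which opens "If myopathy occurs without an obvious reversible precipitating factor", is not met, and neither is its second limb.
- (b) The same, but with no evident reversible cause or with statin myopathy suspected. Both texts call for stopping, so there is no conflict.
- (c) ALT above 3xULN twice, 48 hours or more apart, reversible cause evident, statin liver disease not suspected. Item 4 recommends withdrawal. Appendix C's condition is not met.
- (d) ALT above 3xULN twice in succession, less than 48 hours apart, no reversible cause evident. Appendix C's condition is met. Item 4's criterion is not.

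**Step 4: can the reader resolve it?** For CK, the cross-reference is correct but leads to the differing text. For ALT, it leads to Appendix B, where there is nothing to compare. No precedence clause decides either case.

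**The case against.** The strongest reply is that the conflict is narrow and the appendices are headed as guidance. Section 3.3.5.1 carries the heading for discontinuation criteria, so a natural reading is that it sets the rule and Appendices C and D add work-up. Appendix D never says that stopping is limited to its two conditions and never tells a site to continue. Its second limb is met by mere suspicion of a statin cause, and it requires immediate physician action when CK exceeds 10xULN. This shrinks the CK conflict to case (a). It does not remove it, because the protocol nowhere states that reading and Appendix D attaches its condition to the very event that item 3 treats unconditionally.

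On ALT, much of the reply stands. Both texts only recommend, so the physician keeps discretion under either. Appendix C suggests repeating liver tests after perhaps 4 to 10 days, which already satisfies 48 hours, so case (d) needs an early repeat. The miscited appendix is mitigated by correct references in Section 4.7.2.1 and in the unscheduled-visits text of Section 3.1.

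Two stronger readings are tempting. First, a reader might infer that stopping the statin rather than study medication acts differently by arm, because in the combination phase rosuvastatin patients take ezetimibe as a separate tablet and simvastatin patients take one fixed-dose tablet. The documents do not carry this far: both appendices go on to restrict restarting study treatment, which presupposes that study treatment was stopped, and nothing provides for ezetimibe alone. What remains is loose terminology.

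Second, a reader might infer that open-label sites would choose the rule by arm, distorting the discontinuation comparison or feeding monotherapy LDL-C values into the primary LOCF analysis. Nothing in the documents shows such a pattern or allows its size to be estimated, and Section 6.4 plans no significance tests on adverse events.

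**Conclusion.** The point holds as an internal inconsistency. The main part is the CK instruction: Section 3.3.5.1 item 3 and Appendix D differ for a symptomatic patient with CK above 10xULN, a reversible cause and no suspicion of statin myopathy. The ALT mismatch is secondary, since it lies between two recommendations, and the Appendix B citation is a plain reference error.

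The size cannot be put in numbers: the documents give no expected count of such events. That they will be few is an assumption. The conclusion also assumes that a site would take Appendix D's condition as meaning what it says, so that an unmet condition carries no instruction to stop. No effect on the treatment comparison or on the primary result is claimed. The reason to act is that the text concerns when treatment stops for a key safety event and can be made unambiguous at almost no cost.

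**What to change.** Reconcile Section 3.3.5.1 item 3 with Appendix D, and item 4 with Appendix C, so that each event has one rule worded identically in both places. For each rule, settle whether a reversible-cause condition applies and, for ALT, whether a minimum gap between the two values applies. Align the list of muscle symptoms at the same time. Use one term throughout for what is stopped; study medication is the term Section 3.3.5.1 already uses. Change item 4's reference from Appendix B to Appendix C. Which rule applies is a decision for the sponsor's physicians, and none is proposed here.

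The cost is a protocol clarification, handled through the change procedure in Section 7.4. Design, sample size, visit schedule and analysis are unaffected.
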